5.4 Dose Modifications

All toxicities should be graded according to the NCI Common Terminology Criteria for Adverse Events (CTCAE) version 4.0. A copy of the CTCAE version 4.0 can be downloaded from the CTEP web site (<http://ctep.cancer.gov>) .

5.4.1 Dose Modification for Cytarabine – Arm C Consolidation

For patients \geq 70 years of age the cytarabine dose is identical but the patient will receive one dose daily for a total of 6 doses (days 1-6).

Patients should have a daily creatinine and total bilirubin. The dose of cytarabine will be adjusted. The dose of cytarabine will be adjusted if there is a change in the serum creatinine or bilirubin during that cycle after the start of therapy.

Serum Creatinine (mg/dL)	Serum Total Bilirubin	Dose (mg/m ²)
< 2	< 3	1500
> 2 (or an increase of > 0.5 mg/dL from baseline)	< 3	750
> 3	< 3	500
Any	> 3	500

Modified from Smith, et al. JCO 15:833

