3.2.8 Maintenance Criteria, Step 3 for Arms E and F

3.2.8.1 Maintenance should commence within 60 days of recovery of peripheral blood counts after Consolidation Cycle 2. Patients must begin Consolidation Cycle 2 within 60 days of recovery to be eligible for further therapy.

3.2.8.2 Patients must have maintained peripheral blood evidence of a remission as defined in Section [6](#) and must have a CR or CRi, confirmed on restaging BM aspirate and biopsy and cytogenetic analysis.

3.2.8.3 Patients must have an ECOG performance status of 0 -2.

3.2.8.4 Patients must have resolved any serious infectious complications related to Consolidation Cycle 2.

3.2.8.5 Any significant medical complications related to Consolidation Cycle 2 must have resolved.

3.2.8.6 Patients must have a total serum bilirubin \leq 1.5 x ULN and a serum creatinine \leq grade 1. The values must be obtained within 48 hours prior to randomization.

NOTE: If total bilirubin is 2-3 mg/dL, but direct bilirubin is normal, then the patient will be considered eligible.

3.2.8.7 The ANC must be $>$ 1000 mm³ and the platelet count $>$ 75,000 mm³ prior to starting every cycle of treatment with decitabine. Decitabine may be delayed for up to 4 weeks between cycles (i.e. may be administered as infrequently as q8 weeks) while waiting for counts to recover.

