5.6 Duration of Therapy

Patients will receive protocol therapy unless:

- Extraordinary Medical Circumstances: If at any time the constraints of this protocol are detrimental to the patient's health, protocol treatment should be discontinued. In this event submit forms according to the instructions in the E2906 Forms Packet.
- Patient withdraws consent.

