- 2 It is required that complete blood counts be obtained every 4 weeks for the first twenty-four months after the conclusion of consolidation therapy. Complete blood counts should be obtained every three months in the third year. The frequency in subsequent years is at the discretion of the investigator.
- 3 During the administration of daunorubicin or high-dose cytarabine the serum creatinine and total bilirubin are required daily to adjust dose of medications. After the administration of chemotherapy the values must be determined and reported at least weekly or more frequently as clinically indicated.
- 4 A bone marrow is required on day 12-14 (+/- 1 day) to assess whether the patient has achieved an aplastic BM and will receive GM-CSF or G-CSF or a repeat course of induction. Subsequent marrows until recovery of peripheral blood counts are at the discretion of the treating physician. An outcome BM must be performed no sooner than day 28 and no later than day 56 to determine response to induction therapy at the time of recovery of ANC to >1000 & platelets (>100,000) or if the patients is suspected to have residual AML, or if no further recovery is expected (e.g. plateau in platelet recovery).
- 5 If the cardiac ejection fraction cannot be obtained due to weekend or holiday then patients may be enrolled provided there are no clinical signs or there is no history of significant cardiovascular disease and a measurement of cardiac ejection fraction will be performed within 5 days of study enrollment.

6 Prior to each dose of cytarabine during consolidation for patients randomized to Arms A and C.

Rev. 2/13 7 The Cardiac Ejection Fraction must be measured prior to Induction. For patients on Arm A, a repeat measurement is recommended before receiving re-induction (if indicated). Repeat measurement prior to Consolidation Cycle 1 (Arms C & D) is recommended per institutional guidelines and as clinically indicated. **For patients who proceed to Arm G (Allogeneic stem cell transplantation) a repeat measurement of Cardiac Ejection Fraction must be performed after recovery from last cycle of chemotherapy and prior to start of transplant conditioning regimen**

Rev. 2/12 8 Routine bone marrow aspirate and biopsy is required every 3 months during maintenance and observation (Arms E and F) for first 24 months.

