8.1.5 Dose Specifics

Induction Arm A

100 mg/m²/day by 24 hour continuous infusion for 7 days (days 1-7).

Consolidation I

1500 mg/m² as a one hour intravenous infusion every 12 hours for a total of 12 doses (days 1-6) for patients < 70 years of age, or a total of 6 doses for patients ≥ 70 years of age. See Section [5.4.1](#) for dose modifications for Consolidation I. See Section [5.6.3](#) for duration of Consolidation II therapy.

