9.5 Design Changes

Following a pre-planned interim analysis of primary endpoint OS, accrual to Step 1 of this study was suspended on February 23, 2015 based on DSMC's recommendation, due to differences in overall survival favoring standard daunorubicin and cytarabine compared to clofarabine for induction and consolidation. By that time, 727 patients had been accrued to this study.

Among those 727 patients, 120 (16.5%) entered the second randomization. The original protocol design requires 172 patients to be randomized to either the decitabine arm or the observation arm (number of DFS events needed 140), in order to have 90% power to detect approximately a 36% reduction in the DFS hazard rate in the decitabine maintenance therapy arm at the significance level of 0.1.

We plan to reopen the study to accrue additional 52 patients to the second randomization, to finish the accrual goal of 172 patients. This requires about 74 CR/CRI Patients to be pre-registered after their induction therapy. Patients will receive consolidation while on study and then will be randomized to receive either decitabine maintenance treatment or observation, stratified on the induction therapy, cytogenetics and age. Based on the accrual rate of the first 120 randomized patients, we anticipate the additional accrual could be completed within 1.8 years. The final analysis will be performed at 2 years of follow-up after the completion of the accrual. Based on the event rate observed, at that time, 125 DFS events could occur. The study will have approximately 90% power to detect a 37% reduction in the DFS hazard rate in the decitabine maintenance therapy arm, using a one-sided log-rank test at the significance level of 0.1. The half width of two-sided 80% confidence interval on the log hazard ratio (decitabine /observation) will be about 0.23. The half width of two-sided 95% confidence interval on the log hazard ratio (decitabine /observation) will be about 0.35.

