Prior to the study reopen, as the study has reached 60% information for the maintenance comparison (Arms E vs. F), an interim analysis will be performed and the maintenance randomization will be monitored for early stopping in favor of null hypothesis by computing the conditional power. The conditional power will be calculated given the current data, assuming the study will continue until 125 events of the maintenance comparison is reached. If the conditional power is higher than 0.7, the study will be reopen to pre-register 74 CR/CRI patients and accrue additional 52 patients to the second randomization. The cutoff of conditional power is set high, as we want to reopen the study only if there is a good chance of a positive result.

If the conditional power is lower than 0.7, the study will be closed permanently. No more patients will be accrued. Based on the current event rate of the 120

patients, the events are anticipated to be accumulated very slowly. Therefore, the final analysis of the maintenance comparison will be performed at six months after the interim analysis. Based on the current event rate, at that time, we assume 90 DFS events could be observed. With 90 events, the study will have approximately 85% power to detect a 36% reduction in the DFS hazard rate in the decitabine maintenance therapy arm, using a one-sided log-rank test at the significance level of 0.15. The half width of two-sided 70% confidence interval on the log hazard ratio (decitabine /observation) will be about 0.22. The half width of two-sided 95% confidence interval on the log hazard ratio (decitabine /observation) will be about 0.41.

Rev.2/13

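### In the Arm C cytarabine table (Section 5.4.1), a creatinine rise above 0.5 mg/dL to a value still below 2 matches both the 1500 and the 750 mg/m² rows; 750 is almost certainly meant.

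*Combined protocol and SAP*

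**What the plan says.** Section 5.4.1 sets the cytarabine dose in Arm C consolidation by serum creatinine (mg/dL) and total bilirubin. The rows read as follows:

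| Row | Creatinine | Bilirubin | Dose (mg/m²) |
|---|---|---|---|
| 1 | below 2 | below 3 | 1500 |
| 2 | "> 2 (or an increase of > 0.5 mg/dL from baseline") | below 3 | 750 |
| 3 | above 3 | below 3 | 500 |
| 4 | any | above 3 | 500 |

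The sentence above the table says: "The dose of cytarabine will be adjusted if there is a change in the serum creatinine or bilirubin during that cycle". Section 8.1.5 refers the reader to 5.4.1 "for dose modifications for Consolidation I" and adds no rule of its own. Sections 5.1.6 and 5.5.1 repeat the schedule (12 doses over days 1–6 at age 60–69, 6 doses at age 70 and above) without a renal rule. Footnote 3 to the calendar in Section 7.1 makes the table the daily working rule: "During the administration of daunorubicin or high-dose cytarabine the serum creatinine and total bilirubin are required daily to adjust dose of medications".

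**The concern.** Rows 1 and 2 are not mutually exclusive. Row 1 looks only at the absolute creatinine, while row 2 also looks at the change from baseline. A patient whose creatinine climbs by more than 0.5 mg/dL but stays below 2 qualifies for full dose under one row and half dose under the other. Nothing in the protocol says which row governs.

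Someone reading the table from the top meets the full-dose row first and could stop there. That error runs in the unsafe direction: twice the intended dose, in patients aged 60 or older, during the early renal decline that the rise clause is there to catch. The overlap is widest at low baselines, and the entry rules favour low baselines. Induction requires creatinine of 1 mg/dL or less, or a calculated GFR of at least 60 mL/min (3.2.6.7). Consolidation requires creatinine of grade 1 or less (3.2.7.7).

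**Working it through.** The plan states no figure to reproduce here. The check reads the four rows as literal conditions and lists which of them each value meets.

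**Where rows 1 and 2 overlap (bilirubin below 3).** Row 1 needs creatinine below 2. Row 2 is met by creatinine above baseline + 0.5. Both hold when baseline + 0.5 < creatinine < 2.0, an interval that is empty once the baseline reaches 1.5. In steps of 0.1 mg/dL:

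| Baseline | Values matching both rows | Count |
|---|---|---|
| 0.7 | 1.3–1.9 | 7 |
| 1.0 | 1.6–1.9 | 4 |
| 1.3 | 1.9 | 1 |
| 1.4 or above | none on this grid | 0 |

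**Which reading gives the rise clause a purpose.** Compare the table with and without the clause, over the same 0.1 steps.

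- If row 1 prevails, the clause matters at one value only, creatinine 2.0 (baselines 0.7–1.4). From baseline 1.5 it never matters.
- If row 2 prevails, it matters at 8, 5 and 2 values for baselines 0.7, 1.0 and 1.3. These are the overlap counts plus the value 2.0.

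A clause that acts at a single exact value would have almost no function. In addition, 1500 is the unadjusted dose, and the lead-in says the dose is adjusted on a change. Both points indicate 750.

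**Size of the error if row 1 is followed.** Each affected dose carries an excess of 1500 − 750 = 750 mg/m².

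- Age 60–69, planned 12 × 1500 = 18,000 mg/m². Rise seen before day 2 dosing: 10 × 750 = 7,500, and 7,500 / 18,000 = 41.7%. Rise first seen before day 6 dosing: 2 × 750 = 1,500, and 1,500 / 18,000 = 8.3%.
- Age 70 and above, planned 6 × 1500 = 9,000 mg/m². The same cases give 5 × 750 = 3,750 (41.7%) and 1 × 750 = 750 (8.3%).

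**Other loose edges in the table.** Creatinine above 3 with bilirubin below 3 meets rows 2 and 3 (750 and 500); the lower dose is evidently meant. Two exact values meet no row: creatinine 2 with a rise of 0.5 or less (such as 1.6 to 2.0) while bilirubin is below 3, and bilirubin 3.

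**Remaining use of the table.** Section 9.5 reports that Step 1 accrual is suspended and makes further accrual conditional: "If the conditional power is higher than 0.7, the study will be reopen to pre-register 74 CR/CRI patients". Below 0.7 no more patients enter, so there are no new cycles from new patients. If the study reopens, "Patients will receive consolidation while on study", with two cycles planned. The upper count is 74 × 2 = 148 cycles. The lower count is 52 × 2 = 104, taking only the 52 patients expected to reach maintenance randomization, which follows the second cycle (3.2.8.1: "Maintenance should commence within 60 days of recovery of peripheral blood counts after Consolidation Cycle 2"), and none for the other 22. Both counts assume every such cycle is Arm C cytarabine, which Section 9.5 does not say.

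**After the correction.** With row 1 limited to a rise of 0.5 or less, no grid value matches both 1500 and 750. For example, 0.8 to 1.3 gives 1500 only and 0.8 to 1.4 gives 750 only.

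**The case against.** The strongest reply is that there is only one sensible reading. The specific rise clause would be taken to override the general row 1, and going to the most restrictive matching row settles both overlaps in the table. Harm would require a physician who checks creatinine daily in order to set the dose to see the rise, pass over row 2 and still give full dose.

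There are also safeguards. Cerebellar checks precede each consolidation dose (7.1, footnote 6), and Section 5.6 provides for stopping treatment: "If at any time the constraints of this protocol are detrimental" to the patient's health. Nothing in the documents shows that any site misread the table. The 42% stacks several unfavourable conditions, and the cycle counts are cycles in which the table might be used, not cycles with a creatinine rise. The unmatched exact values depend on strict inequality signs. A symbol is garbled elsewhere in the available text (6.6.6), although the neighbouring daunorubicin table in 5.4.2 keeps its ≤ sign.

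Most of this stands and limits the weight of the point: intent is clear, the frequency is unknown and could be zero, and the backstops are real. It does not remove the defect. Neither backstop supplies a dose, the precedence convention is written nowhere, and the main overlap would remain even if row 1 read 2 or less.

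**Conclusion.** The concern holds. With bilirubin below 3 and a baseline below 1.5 mg/dL, the table as written assigns two doses to any creatinine between baseline + 0.5 and 2.0. The intended dose is almost certainly 750 mg/m², so this is a defect of wording and not an open clinical question.

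Its size is a factor of two for each dose given under the literal row 1 reading. Per cycle, the excess runs from 8% of the planned dose (rise first seen before day 6 dosing) to 42%. The upper figure requires the rise to be seen before day 2 dosing, creatinine to stay in the band through day 6, and the site to give 1500 each time. The documents do not say how often such rises occur.

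No endpoint, sample size, error rate or analysis is affected. Urgency depends on whether the study reopens and whether the reopened consolidation uses Arm C cytarabine. The point should be corrected, but it does not threaten the trial's conclusions.

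**What to change.** Either reword row 1 as *creatinine < 2 and rise ≤ 0.5 mg/dL from baseline*, or add beneath the table *if more than one row applies, give the lowest dose*. Either removes the conflict between 1500 and 750. The added note also settles creatinine above 3, so it is the more complete choice.

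The study team should separately assign and confirm the dose at creatinine exactly 2 with a rise of 0.5 or less, and at bilirubin exactly 3; the documents do not settle either. The core change is one line in one table, with no added visits, tests or patients.

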5.4.2 Dose Modification for Daunorubicin During Induction Cycle II- Arm A

Patients who do not achieve aplasia with Cycle I are eligible for a second cycle of induction. The total bilirubin should be determined on the days of the administration of daunorubicin. The dose of daunorubicin is adjusted according to the following table.

If Total Bilirubin	Administer % of Daunorubicin Dose
\leq 1.5 mg/dL	100%
1.5 to 3 mg/dL	75%
3.1 to 5 mg/dL	50%
> 5 mg/dL	No Daunorubicin

Reference: The Chemotherapy Source Book, second edition. Perry, M.
Publisher: Williams and Wilkins

5.4.3 Decitabine Arm F Maintenance

There are no planned dose reductions in decitabine. Patients unable to receive treatment on schedule (i.e. planned q4 weeks, but delays up to 4 weeks allowed) due to cytopenias or persistent side effects will discontinue decitabine and subsequently be observed per the 'observation' group (Arm E), although they will be analyzed on an 'intention to treat' basis as having been assigned to Arm F.

5.4.4 Clofarabine Dose Modifications – Arm B Induction and Re-induction, and Arm D

Rev. 2/13

5.4.4.1 Hematologic (Blood/Bone Marrow) Toxicity

Patients who achieve a CR or CRi should receive the consolidation cycle no sooner than 28 days from Day 1 of the previous induction or re-induction cycle, provided their peripheral blood counts have recovered (ANC $\geq 1.0 \times 10^9/l$ and platelet count $\geq 100 \times 10^9/l$ (or $\geq 50 \times 10^9/l$ if previously achieved CRi). If the peripheral count recovery is delayed beyond Day 42 from Day 1 of the prior induction or re-induction cycle and the delay is presumed to be secondary to the induction or re-induction therapy, the clofarabine dose for the consolidation cycle, if administered, must be reduced by 25% for all subsequent doses.

5.4.4.2 Non-Hematologic Toxicity

Dose Modifications During the Treatment Period (Intracycle Dose Modifications)

Patients who experience a grade 3 or greater drug-related non-hematologic toxicity or asymptomatic grade 2 serum creatinine or serum total bilirubin during clofarabine administration should have clofarabine withheld until recovery to baseline or grade 1 before resuming treatment. Dose omissions due to the above noted toxicities that occur during the drug administration period will only be made up if the toxicity resolves such that a dose delay does not exceed 48 hours. If study drug administration resumes, proceed at 25% dose reduction for all subsequent doses and cycles of clofarabine. Only one interruption during study drug(s) administration is allowed per treatment cycle. Excluded from this rule are:

- Grade 3 or greater anorexia, rash/desquamation, infection, transient isolated elevations in hepatic transaminases (AST and ALT) or alkaline phosphatase do not require withholding or reducing clofarabine.
- Grade 3 or greater nausea, vomiting, diarrhea, or mucositis may require that the clofarabine be withheld. This decision should be guided by the investigator based on best clinical judgment. If clofarabine is being held it can be restarted if, for these toxicities, recovery to grade 2 or less occurs within 48 hours (with or without supportive care) These toxicities do not require dose reduction of clofarabine.

5.4.5 Dose Modifications for Subsequent Cycles of Study Treatment

Clofarabine doses for re-induction and consolidation cycles will be modified (delayed/reduced) or discontinued for non-hematologic toxicity according to the criteria listed in the table:

Criteria for Treatment Clofarabine Delays, Dose Reductions, and Discontinuations in Patients Experiencing Non-Hematologic Toxicities for Re-Induction and Consolidation Cycles

Non-Hematologic Toxicities	
Description of Event	Treatment Delays, Dose Reductions, or Discontinuations
Infection any grade	Re-induction Cycle: No delay is required. Consolidation Cycle: If a patient develops a clinically significant infection of any grade, consideration should be given to delaying the consolidation cycle until the infection is clinically controlled (defined as improvement of signs/symptoms related to the infection with appropriate antibiotics or other treatment)—however, the judgment ultimately rests with the investigator. Treatment (ie, subsequent cycle) may then resume without dose reduction. At the discretion of the investigator, prophylactic therapy to prevent recurrence of infection may be instituted as clinically indicated.
Drug-related non-infectious event(s): Grade 2 toxicity	Re-induction and Consolidation Cycles: Initiation of a treatment cycle will be delayed until returned to baseline or \leq Grade 1. If this has not occurred by Day 56 from Day 1 of the treatment cycle, further study drug treatment cannot be administered. No dose reduction is required for subsequent cycles after recovery of Grade 2 toxicities to \leq Grade 1.
Drug-related non-infectious event(s): \geq Grade 2 neurologic toxicity	Re-induction and Consolidation Cycles: The patient's study drug doses are to be re-evaluated in consultation with the PI, and may be reduced or discontinued according to the parameters below defined for a drug-related Grade 2 or higher toxicity.
Drug-related non-infectious, non-neurologic event(s): Grade 3 toxicity	Re-induction and Consolidation Cycles: If toxicity recovers to baseline or Grade 1 by Day 56 from Day 1 of the treatment cycle, study treatment is to be restarted at a 25% dose reduction with no alteration in schedule for clofarabine for all subsequent cycles. If treatment has not resumed by Day 56 from Day 1 of the treatment cycle, further clofarabine cannot be administered.
Drug-related non-infectious event: Grade 4 toxicity	Re-induction and Consolidation Cycles: The patient must not receive additional clofarabine except under extraordinary circumstances and only after consultation with the PI. If study treatment is restarted, toxicity must recover to baseline or Grade 1 by Day 56 from Day 1 of the treatment cycle, and either a 25% or 50% dose reduction with no alteration in schedule for clofarabine should be instituted for all subsequent cycles.

5.5 Supportive Care

All supportive measures consistent with optimal patient care will be given throughout the study.

5.5.1 Cytarabine Consolidation- Arm C- Cycles 1 and 2

Patients must receive corticosteroid eye drops, 2 drops in each eye at least 4 times a day starting on day 1 before the first dose of cytarabine and continuing until at least 48 hours after completion of cytarabine, i.e. for a minimum of 8 days.

Cytarabine Age 60-69 1500 mg/m² as a one hour intravenous infusion every 12 hours for a total of 12 doses (days 1-6) times 2 cycles.

		Age \geq 70 1500 mg/m ² as a one hour intravenous infusion every 24 hours for a total of 6 doses (days 1-6) times 2 cycles.
	Corticosteroid	2 drops in each eye, 4 times a day for 10 days. The eye drops should be applied within one hour of the administration of high dose cytarabine.
	GM-CSF	250 mcg/m ² /day by intravenous or subcutaneous injection starting one day after the last dose of cytarabine through recovery of absolute neutrophil count (ANC) \geq 500 cells/mcL is sustained for 3 consecutive days. The dose may be rounded to the nearest vial size.
	OR G-CSF	5 mcg/kg/day by either intravenous or subcutaneous injection starting one day after the last dose of cytarabine, through recovery of absolute neutrophil count (ANC) \geq 500 cells/mcL is sustained for 3 consecutive days. The dose may be rounded to the nearest vial size.
	OR Pegfilgrastim	6mg SC on day 7 (1 day after completing the last dose of cytarabine).
Rev. 2/12	5.5.2	
Supportive Care with GM-CSF, G-CSF & Prophylactic Antibiotics for Restaging Bone Marrow
 
Patients who achieve an aplastic BM following the 1st or 2nd course of induction therapy should receive cytokine support with GM-CSF (LeukineTM) at a dose of 250 mcg/m²/day subcutaneously every day until calculated ANC \geq 5000/mcL or discharge from hospital. Alternatively, patients may receive G-CSF at a dose of 5 mcg/kg (rounded to the nearest vial size) at the discretion of the treating physician.
 
Patients should receive an oral Quinolone, Fluconazole, and Acyclovir to prevent infection once the ANC drops below 1000 beginning sooner than day 7 of induction.

Rev. 2/12	5.5.3	Arm D Clofarabine Consolidation
Rev. 2/12		
Patients should receive an oral Quinolone, Fluconazole or equivalent based on institutional standard, and Acyclovir to prevent infection once the ANC drops below 1000 mm³.
 
GM-CSF 250 mcg/m²/day by intravenous or subcutaneous injection starting one day after the last dose of clofarabine through recovery of absolute neutrophil count (ANC) \geq 500 cells/mcL is sustained for 3 consecutive days. The dose may be rounded to the nearest vial size.

Rev. 2/12

OR
G-CSF 5 mcg/kg/day by either intravenous or subcutaneous injection starting one day after the last dose of clofarabine, through recovery of absolute neutrophil count (ANC) \geq 500 cells/mcL is sustained for 3 consecutive days. The dose may be rounded to the nearest vial size.

OR
Pegfilgrastim 6 mg SC on day 6 (1 day after completing the last dose of clofarabine).

5.5.4 **Arm G** Supportive Care for Allogeneic Transplant

Rev. 2/13

NOTE: Patients must be premedicated with acetaminophen 650 mg P0, diphenhydramine 25-50 mg P0/IV prior to thymoglobulin, and methylprednisolone 1 mg/kg at initiation and midway through thymoglobulin administration each day.

Patients will be evaluated on an outpatient basis for evidence of toxicity, in particular graft vs. host disease (GVHD) and cytopenias.

GVHD Prophylaxis

Tacrolimus dosing is to be based on target serum levels of 5-10 ng/mL. **Serum levels are not to exceed 15 ng/mL.** Tacrolimus is to be initiated on Day -2 with a suggested starting dose of 0.03 mg/kg P0 BID (Institutional standard allowed if equivalent). Begin tapering between Day +90 to +120 in the absence of GVHD as tolerated with a goal of stopping by Day +150 to +180. The rate of taper will be adjusted for the presence of signs and symptoms of GVHD. In patients who are unable to take oral tacrolimus, the intravenous dose is generally 1/4 to 1/3 of the oral dose.

Please note that concurrent use of agents such as itraconazole, voriconazole or fluconazole (at doses $>$ 200 mg) may inhibit the metabolism of tacrolimus, and thus increase tacrolimus levels. Hence, it is recommended to check tacrolimus levels twice weekly when these agents are initiated concurrently. In addition, the initial dose of tacrolimus may be decreased according to institutional policies.

Methotrexate 5 mg/m²/day IV on Days +1, +3, +6 and Day +11. Hydrate intravenously and induce diuresis. Methotrexate will be held if the serum creatinine $>$ 3.0 mg/dL. If the creatinine level is $>$ 1.5 mg/dL, then administer leucovorin 10 mg IV or P0 q6 hours for four doses beginning 24 hours after methotrexate.

Rabbit antithymocyte globulin (Thymoglobulin) at 2.5 mg/kg/day IV over 6 hours x 3 doses on Days -4 through -2. Patients must be premedicated with acetaminophen 650 mg P0, diphenhydramine 25-50 mg P0/IV, and methylprednisolone 1 mg/kg at initiation and midway through thymoglobulin administration each day. After the first dose, subsequent administration of antithymocyte globulin may be infused over 4 hours.

Patients with progressive disease will have met the primary study endpoint and will be removed from protocol therapy. Such patients may receive additional treatment at the discretion of the investigator, although patients will be followed for response to further therapy, survival and new primary malignancies.

Mucosal Evaluation and Care: Mucositis is expected to be very mild with this chemotherapy regimen. Stomatitis and esophagitis due to herpes virus may be confused with drug-induced mucositis and viral cultures should be obtained frequently. Patients with a history of herpes simplex infection or seropositivity will receive acyclovir 200-400 mg PO TID Days -3 through Day + 100. Valacyclovir 500 mg P0 QD may be used instead of acyclovir. Prophylaxis may be extended beyond Day +100 at the discretion of the treating physician.

Candida Prophylaxis: Fluconazole or itraconazole 200-400 mg P0 daily or voriconazole 200-300 mg P0 twice daily (or 3-6 mg/kg IV q12 hours) on Days -2 through +100 per institutional standards. Low dose amphotericin B (10-20 mg/day) IV also may be used.

Pneumocystis Pneumonia (PCP) Prophylaxis: In an attempt to prevent PCP, cotrimoxazole (Bactrim®) will be administered to all patients as one double strength tablet BID on 2 days weekly, beginning on Day +28 through Day + 100. If, at this time, CD4 lymphocytes are < 200/ μ L, then prophylaxis should be continued until CD4 lymphocytes are \geq 200/ μ L. Patients allergic to cotrimoxazole should receive dapsone or inhaled pentamidine instead. In patients who develop chronic GVHD, PCP prophylaxis should be extended at the discretion of the physician.

CMV Infections: No routine prophylaxis for CMV will be initiated. Surveillance for CMV using CMV Ag (e.g.. immunofluorescence) or CMV PCR (or Digene Hybrid Capture® assay or equivalent) is required weekly beginning on Day +7 through Day +100, and then every other week through Day + 180. Patients with positive CMV PCR or positive CMV Ag'emia should receive treatment with ganciclovir 5 mg/kg IV BID x 14 days (or appropriate doses of valganciclovir or foscarnet).

DOSE MODIFICATIONS AND MANAGEMENT OF TOXICITY

Tacrolimus

Tacrolimus may cause hypertension, renal insufficiency (usually reversible), seizures, liver function abnormalities, hemolytic uremic syndrome (rare), hyperglycemia, and hypomagnesemia.

Tacrolimus dose adjustments will be made to achieve target trough levels of 5-10 ng/mL. Serum levels are not to exceed 15 ng/mL.

Methotrexate

Methotrexate may cause mucositis and cytopenias. In the presence of worsening renal insufficiency or the development of effusions or ascites, the addition of leucovorin is permitted at the discretion of the

physician. If the creatinine is > 1.5 mg/dL, leucovorin 10 mg IV or P0 may be given every 6 hours for four doses beginning 24 hours after methotrexate. Methotrexate will not be given if the creatinine is > 3.0 mg/dL. Individual doses of methotrexate will not be altered.

Graft Versus Host Disease

It is expected that some patients will develop mild-moderate graft versus host disease. It is precisely this effect that may be associated with an antineoplastic outcome.

The diagnosis of acute graft versus host disease rests on clinical presentation (rash, diarrhea, liver function abnormalities) and histopathologic evidence via skin, gastrointestinal, or liver biopsy. Chronic GVHD is associated with rash, sicca syndrome, hepatitis. In addition grade 2-4 GVHD or extensive chronic GVHD will be treated with methylprednisolone 2 mg/kg/day and subsequently tapered according to institutional standard. The ultimate treatment approach, i.e., the addition of cyclosporine, tapering of immunosuppressive medications, etc., will be left to the discretion of the transplant or hematology/oncology physician according to institutional standard allogeneic guidelines for the management of these conditions. The following tables should be used for reporting these toxicities.

Clinical Grading of Acute GVHD

Organ Grade	Skin Changes	Bilirubin (mg/dL)	Gut Changes (diarrhea [ml/day])
0	No rash	< 2.0	None
1	Erythematous macular rash over < 25% body surface	2 - <3.0	> 500 - \leq 1000
2	Over 25-50% of Body surface	\geq 3 - <6	> 1000 - \leq 1500
3	\geq 50% body surface	\geq 6 - < 15	> 1500
4	Bullae, exfoliation Ulcerative dermatitis	\geq 15	Severe abdominal pain with or without ileus

Organ Grade (see table above)			
Skin Changes	Hepatic	Gut Changes	Overall Grade
0	0	0	0
1 or 2	0	0	1
1, 2, 3	1	1	2
2 or 3	2 or 3	2 or 3	3
Patients with Grade 4 toxicity in any organ system are considered overall Grade 4.			

Clinical Grading of Chronic GVHD

Limited Chronic GVHD:

1. Localized skin involvement,
and/or
2. Hepatic dysfunction due to chronic GVHD.

Extensive Chronic GVHD:

1. Generalized skin involvement,
or
2. Localized skin involvement and/or hepatic dysfunction due to
chronic GVHD

Plus

- 3a. Liver histology showing chronic aggressive hepatitis, bridging
necrosis, or cirrhosis, **or**
- 3b. Involvement of eye (Schirmer's test with less than 5 mm wetting),
or
- 3c. Involvement of minor salivary glands or oral mucosa
demonstrated on labial biopsy, **or**
- 3d. Involvement of any other target organ.

Rev. 2/13

Instructions for Dosing by Corrected Body Weight (Arm G)

High-dose chemotherapy can adversely impact the outcomes of obese patients when dosing is performed according to actual body weight. **Therefore, all therapy (including methotrexate and tacrolimus) and growth factor drug doses will be determined using a corrected body weight formula. The corrected body weight is calculated based on the following formula with all weights in kg:**

Corrected Weight = (0.25)(actual weight - ideal weight)+(ideal weight)

Thus, for patients whose actual weight is > 150% of ideal, their "actual" weight will be capped at 150% of ideal (i.e., their corrected weight will be 112.5% of ideal). For patients whose actual weight is less than ideal, use their actual weight as the corrected weight.

